1.1 General Approach

The final statistical design for this trial was informed by the need to learn as rapidly as possible from the data during the pandemic while simultaneously managing the risk of drawing erroneous conclusions. Additionally, the DSMB requested that the analysis plan be modified to reduce the number of interim analyses and to anticipate the possibility that the study might need to enroll a larger number of subjects than initially proposed. This requires a framework for decision-making that does not demand that all possible looks of the data are prespecified, as is required of approaches based on p-values. Two approaches which offer the needed flexibility are the likelihood and Bayesian frameworks, which are closely related. The likelihood approach uses the likelihood function to generate point-estimates and interval estimates of the treatment effect. Moreover, competing hypotheses are compared with likelihood ratio (LR), to measure the relative strength of evidence for the null and alternative hypotheses. Because it retains its meaning and reliability regardless of the number of looks at the data or endpoints under consideration^{1,2}, the LR has been successfully implemented in clinical trials, including in trials with continuous monitoring or sequential methods.^{3,4} The closely related Bayesian framework has also been successfully implemented in COVID-19 clinical trials.⁵ The Bayesian framework combines the likelihood function with a researcher prior distribution in order measure the strength of evidence for competing hypotheses on an absolute, probability scale rather than the relative scale of the likelihood approach. We acknowledge that the Bayesian approach could have also been implemented as a decision-making framework in this study (and similar studies for which the schedule of interim analyses is not fixed). However, to avoid the ambiguous task of eliciting a prior distribution, we opted to focus on the likelihood alone.

Decision making using the likelihood approach in a clinical trial centers on three quantities: the point estimate of the treatment effect (an odds ratio, for example), a corresponding interval estimate, and a single number summary---the likelihood ratio---which measures the relative evidence for one hypothesis compared to another. These three quantities are not unlike the point estimate, 95% confidence interval, and p-value that are generated in frequentist analyses. In fact, the point estimates of often identical, and the interval estimates are often similar. The LR and the p-value, however, are distinct measures of evidence. The LR is a ratio: the density of the trial data if the treatment works (alternative hypothesis) divided by the density of the trial data if the treatment does not work (null hypothesis). A LR of 1 indicates the data are neutral; neither hypothesis is supported over the other. Large LR are evidence in support of the treatment working while small LR are evidence in support of the null. In short, the LR level of evidence is based on comparing the likelihood of the data under two competing models – the alternative hypothesis and the null hypothesis. This is different to using a p-value as the level of evidence because the p-value essentially compares what actually happened in the trial to what might have happened in the trial if it were repeated infinitely and the null hypothesis were true. Because it is impossible to compute what might have happened if the rules for decision making are not fully predefined, using a p-value for decision making is not well suited for a trial like this one in which DSMB requests and pandemic circumstances prompted design changes. The LR approach on the other hand, is based on a relative likelihood of observed outcomes under two competing models at the same point in time making it especially appropriate for settings where pre-specification of the timing or frequency of sequential analyses is not possible. In this study, a LR of 7 or larger in favor of treatment is considered sufficient evidence to assert that the treatment is beneficial.

Even though the LR (instead of the p-value) is the quantity of primary interest for decision making, the analysis plan does control type 1 error. Sequential likelihood ratio tests of two prespecified hypotheses have a natural bound on type 1 error of $1/k$ where k is the threshold for asserting efficacy. In this study, the combination of the stopping rule for mortality and the large number of subjects accrued before the first analysis for efficacy result in a bound on type 1 error well within traditional levels of 0.05 as described in detail below.

2. Planned interim analyses for mortality

Initially, this trial included frequent interim analyses with reporting triggers for efficacy, harm, and futility. At DSMB request, the frequency of interim analyses was reduced, and reporting triggers were replaced with a single stopping rule for harm based on a comparison of day 15 mortality between placebo and intervention arms. While the DSMB requested that a flexible sample size be accommodated in our design, they did not request formal rules for extending the study because the context for decision making in a pandemic is unknown, further emphasizing the utility of the LR approach.

The three interim analyses are planned to occur after day 15 follow-up data collection is completed for 150, 450, and 750 study subjects. Adverse events, safety outcomes, protocol deviations, and the primary endpoint will be described grouped by study arm. Initially, the intervention arm and placebo labels will be replaced with generic labels “treatment A” and “treatment B”, and the DSMB Chair may request to unmask the group assignment.

The difference in mortality risk will be calculated, and the one-sided hypothesis that mortality risk in the intervention arm exceeds the mortality risk in placebo will be compared to the null hypothesis of equal mortality risk.

	Hypothesis	
Null	$\Delta \leq 0$	(Treatment is beneficial or neutral)
Alternative	$\Delta > 0$	(Treatment is harmful).
$\Delta = P(\text{mortality among treated}) - P(\text{mortality among controls})$		

The trial will be stopped if the likelihood ratio exceeds the threshold listed below. Generally, the level of evidence required to stop a study for safety concerns is less than the level of evidence required to assert efficacy of the intervention. Likewise, there is not the same level of concern for type 1 error control for safety outcomes as there is for efficacy endpoints; however, the threshold values were selected so that the trial-wise risk of ending early for mortality is 0.1 if the treatment is equivalent to placebo ($\Delta = 0$). To provide context for the LR thresholds listed in the table below, we have also provided α_N , the p-value threshold which approximates the LR threshold if the p-value were calculated from a likelihood ratio test.

N	LR Threshold	α_N
150	6.3	0.0275
450	4.0	0.0479
750	3.3	0.0612

3. Analysis plan for primary endpoint

The data from the clinical trial will be analyzed after follow-up and data lock is completed for all study subjects. The analysis will be intent-to-treat, meaning that patients will be analyzed according to the randomization schedule regardless of the treatment administered. The main result will be an estimate of the treatment effect odds ratio, its likelihood ratio when compared to the null, and the corresponding 1/7 likelihood support interval, all of which will be estimated from a cumulative probability ordinal regression model (CPM) with logit link. The marginal likelihood function for the treatment effect parameter will be the asymptotic regression coefficient distribution; specifically, it will be the normal distribution density function with mean and standard deviation equal to the regression estimates. Likelihood ratios more extreme than 7 will be interpreted as sufficient evidence to assert efficacy. In order to increase study power, the following variables will also be included into the regression:

1. Treatment (1 parameter)
2. Age (2 parameters, restricted cubic spline)
3. Sex (1 parameter)
4. Baseline SOFA score (1 parameter, linear term)
5. Baseline COVID-19 7-point Ordinal Clinical Progression Outcomes Scale score (possible range:3-6) (2 parameters, quadratic)
6. Time from symptom onset in days (2 parameter, non-linear term)
7. Site indicator variables (either as a main effect or as a random effect, depending on the number of sites enrolling patients)

3.1 Model fit

Model fit will be assessed with probability scale residuals and with leave-one-out diagnostics like DFBETAS. If model diagnostics indicate that an alternative link function provides a superior fit, then that alternative link function will be proposed instead.

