8.3 Analysis plan for primary endpoints

The statistical analysis plan (SAP) contains a more complete description of analysis methods, definitions, and sensitivity analyses. In this section, we reprint relevant portions of the SAP.

The data from the clinical trial will be analyzed after follow-up is completed for all study subjects. The analysis will be intent-to-treat, meaning that patients will be analyzed according to the randomization schedule regardless of the treatment administered. The key result of the analysis is an estimate of the treatment effect odds ratio, its likelihood ratio when compared to the null, and the corresponding 1/7 likelihood support interval, all of which will be estimated from a cumulative probability ordinal regression model (CPM) with logit link. The marginal likelihood function for the treatment effect parameter will be the asymptotic regression coefficient distribution; specifically, it will be the normal distribution density function with mean and standard deviation equal to the regression estimates. Likelihood ratios more extreme than 7 will be interpreted as sufficient evidence to assert efficacy. In order to increase study power, the following variable will also be included into the regression:

1. Treatment (1 parameter)
2. Age (2 parameters, restricted cubic spline)
3. Sex (1 parameter)
4. SOFA score (1 parameter, linear term)
5. Baseline COVID-19 7-point Ordinal Clinical Progression Outcomes Scale score (possible range:3-6) (2 parameters, quadratic)
6. Time from symptom onset in days (2 parameter, non-linear term)
7. Site indicator variables (either as a main effect or as a random effect, depending on the number of sites enrolling patients)

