8.3.1 Model fit

Model fit will be assessed with probability scale residuals and with leave-one-out diagnostics like DFBETAS. If model diagnostics indicate that an alternative link function provides a superior fit, then supplementary information will be sent to the DSMB to decide if an alternative link function should be used.

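### The logit link of the primary model can be replaced after the final data are modelled, with no criterion and with a different process in each document

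*SAP*

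**What the plan says.** **Primary model.** SAP section 3 names the treatment odds ratio, its LR against the null and the 1/7 support interval, "all of which will be estimated from a cumulative probability ordinal regression model (CPM) with logit link". Protocol 8.3 agrees: "The key result of the analysis is an estimate of the treatment effect odds ratio". On timing, SAP section 3 states: "The data from the clinical trial will be analyzed after follow-up and data lock is completed for all study subjects".

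**Link clause.** Both documents assess fit with probability-scale residuals and leave-one-out diagnostics such as DFBETAS. If these favour another link, SAP 3.1 says "then that alternative link function will be proposed instead". With the same trigger, Protocol 8.3.1 says "supplementary information will be sent to the DSMB to decide if an alternative link function should be used". Protocol 8.3 introduces its content with "In this section, we reprint relevant portions of the SAP", so the two should match.

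**DSMB access.** Under SAP section 2, the primary endpoint is described by arm at each of the three interim analyses. The labels are coded at first, and "the DSMB Chair may request to unmask the group assignment".

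**Operating characteristics.** The SAP gives a simulated type I error of 0.02 and 80% power at an adjusted odds ratio of 0.73 or lower with 1000 patients. The simulations are described as applying the stopping rule and the analysis plan. No link-selection step is mentioned. The only sensitivity analysis named in SAP 3.3 is per-protocol.

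**The concern.** The final model contains the treatment term and is fitted after data lock, so any judgement about the link comes after the result is available to whoever fits it. The plan does not say what counts as a better fit, which links are candidates, whether the diagnostics are masked, or whether the logit result is still reported. The SAP does not say who proposes the alternative, to whom, or whether it displaces the primary analysis. The protocol gives the decision to a board that will already have seen the primary endpoint by coded arm.

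Two things are at stake. First, the effect measure: under a probit, complementary log-log or log-log link the treatment coefficient is not the odds ratio that the plan defines and powers. Second, the decision: the LR is computed from that coefficient and its standard error, so a different link gives a different LR to set against 7. The bound on type I error in SAP 1.1 and Protocol 8.4.1 is argued for pre-specified hypotheses, and a link chosen afterwards is not pre-specified. The gap extends further, because the ordinal secondary outcomes use the same model with similar fit steps (SAP 6.1, Protocol 8.6.1).

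**Working it through.** **1. The plan's own figures, logit link.** The marginal likelihood is normal, so the LR of the estimate against the null is exp(z²/2). LR = 7 gives z = √(2 ln 7) = 1.973, a one-sided tail of 0.0243. Adding the mortality stopping rule at 150, 450 and 750 patients gives 0.0239 to 0.0244. The stated 0.02 comes from 1000 simulated trials, with standard error √(0.02 × 0.98/1000) = 0.0044, so it agrees.

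For power, the proportional-odds formula is SE(log OR) = √(12/[N(1 − Σp³)]), where p are the category proportions. The documents do not give these, so Σp³ is an assumption. With N = 1000 and Σp³ = 0.04, SE = √(12/960) = 0.1118, and power = Φ(0.3147/0.1118 − 1.973) = Φ(0.842) = 0.80. The range is 0.808 for seven equal categories, 0.783 at Σp³ = 0.08 and 0.774 at 0.10. The stated 80% is reproduced closely.

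**2. Scale under other links.** One logit-generated dataset of 200,000 with true odds ratio 0.73 gave these exponentiated coefficients: logit 0.735, probit 0.835, complementary log-log and log-log 0.836. The last three are not odds ratios.

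**3. Effect of switching by fit.** Simulated trials had N = 1000, 1:1 allocation, seven categories, one prognostic covariate and four links (logit, probit, complementary log-log, log-log). The best fit was the highest log-likelihood. Assumed control distributions for categories 1 to 7:
- A: 10, 25, 15, 20, 8, 7, 15%
- B: 20, 40, 5, 10, 5, 10, 10%

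The covariate coefficient per SD was 1.0 for A and 0.5 for B with logit truth, and 0.7 with complementary log-log truth. There were 4000, 2500 and 1500 replicates for the logit null, complementary log-log null and power rows respectively. The mortality rule was omitted.

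| Setting | LR > 7 for benefit, logit fixed | LR > 7, best-fitting link | Best fit not logit | Decision differs |
|---|---|---|---|---|
| A, null, logit true | 0.0232 | 0.0238 | 18.2% | 0.25% |
| B, null, logit true | 0.0258 | 0.0280 | 35.8% | 0.38% |
| A, null, comp. log-log true | 0.0284 | 0.0248 | 99.8% | 1.7% |
| A, OR 0.73, logit true | 0.763 | 0.764 | 19.8% | 0.6% |
| B, OR 0.73, logit true | 0.787 | 0.781 | 34.1% | 1.9% |

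A third assumed distribution (25, 30, 5, 12, 5, 8, 15%; 2000 null trials at each of covariate coefficients 1.0 and 0.5) gave 0.020 and 0.0235 with logit fixed, and 0.0195 and 0.0255 with the best-fitting link.

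The largest shift in type I error is 0.0284 − 0.0248 = 0.0036. The largest shift in power is 0.787 − 0.781 = 0.006. Simulated power below 80% reflects the assumed distributions and covariate strengths and is not evidence against the stated figure.

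**4. Logit when another link is true.** In the third row, fixed logit gave 0.0284. Against 0.0243, with standard error √(0.0243 × 0.9757/2500) = 0.0031, that is about 1.3 standard errors high, so this setting shows no clear loss of error control.

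**The case against.** The strongest reply is that the clause is harmless. Both documents make any change conditional on better fit, and fit-based switching hardly moves error or power. That stands. So do these limits on what may be inferred:

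- **Unblinded switching.** A reader might infer that the link is chosen on unblinded data. The documents do not say so. Coded arms or a fit without the treatment term are not ruled out; masking is simply unspecified.
- **Inflated type I error.** If the link most favourable to treatment could be picked freely, the error in these simulations would be about 0.039 to 0.060, which can exceed the SAP's stated bound of 0.05. That is a ceiling on discretion, not the written rule.
- **Frequent switching.** The 18 to 36% in the logit-true rows counts any likelihood advantage, however small. With the third distribution, an alternative led by any margin in 23 to 38% of trials, by more than 2 log-likelihood units in 2 to 3%, and by more than 5 in at most 0.1%.
- **Bias from 0.73 to 0.84.** This is a change of scale. Nothing says that another link's coefficient would be reported as an odds ratio.
- **Two named deciders.** The SAP names none. Its wording could be read as a proposal that the DSMB then rules on, but nothing in the SAP says so, and the protocol claims to reprint it.

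The sponsor could also say that a poor link matters. That is partly right: with A, null and logit true, always fitting complementary log-log or log-log gave 0.0357 and 0.0335. This supports examining the link, but not an open-ended choice after data lock.

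**Conclusion.** The point holds as a gap in pre-specification and a mismatch between documents. The plan lets the primary effect measure and the model behind the LR > 7 decision change after the final data are modelled, without a criterion and without securing the logit result. It should be corrected because the wording leaves discretion and the correction is nearly free.

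The numerical consequence of a strict fit-based choice is negligible: type I error of about 0.020 to 0.028 either way, and at most about 0.6 percentage points of power. A reader might conclude that the stated 0.02 and 80% are wrong. They are not, for the logit analysis; they simply do not describe a plan with a link-selection step.

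These sizes rest on assumed control distributions and covariate strengths, and on a log-likelihood criterion standing in for the residual and DFBETAS diagnostics that the plan names.

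**What to change.** Put the same rule in SAP 3.1 and Protocol 8.3.1, for example:

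*The cumulative probability model with logit link is the primary analysis and the sole basis for the odds ratio, likelihood ratio, 1/7 support interval and efficacy decision, whatever the model diagnostics show. Alternative links suggested by diagnostics will be reported only as labelled sensitivity analyses.*

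Delete the DSMB link decision from Protocol 8.3.1, list the alternative-link analyses in SAP 3.3, and apply the rule to the ordinal secondary outcomes.

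The cost is a few lines of text, with no patients and no data. The simulations as described need not be rerun, since they mention no link selection. The small downside is that, if logit fits poorly, the primary odds ratio is an average summary and some efficiency may be lost; the sensitivity analyses would show this.

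If the sponsor prefers to keep a switch, both documents should fix the candidate links, a numerical criterion, a fit blind to treatment and one decision-maker acting before unblinding. The logit odds ratio and LR should always be reported, and the simulations rerun with that step included.

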3.2 Missing data

We anticipate rare or no missingness for data points during the patients' in-hospital course. There may be missing data for the COVID-19 7-point Ordinal Clinical Progression Outcomes Scale score after hospital discharge, which relies on phone follow-up. After discharge, distinguishing between category 1 and category 2 on the scale requires speaking to the participant or surrogate about normal daily activities. If the patient is not reached for follow-up phone calls after discharge, the COVID-19 7-point Ordinal Clinical Progression Outcomes Scale score will be classified as category 2 (not hospitalized, but unable to resume normal activities). If the patient is reached for a follow-up call post-charge and reports category 1, this classification of category 1 will be carried forward to future follow-up calls if the patient cannot be reached. For example, if the patient cannot be reached for the Day 8, 15, or 29 follow-up calls, a category 2 score will be reported for all three visits. If the patient is successfully contacted on the Day 8 call and reports category 1, and then the patient cannot be reached for a Day 15 call, the category 1 score from Day 8 will be carried forward to Day 15.

Missing data for a covariate used in the primary model will be multiply imputed using predictive mean matching if number of observations missing covariate values exceeds 5 percent. If fewer than 5% of observations have missing covariate values, missing values will be imputed with a single conditional mean.

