7.3 Assessments Following Hospital Discharge

7.3.1 Acute Care Follow-up

For participants discharged to home or a post-acute care facility (e.g., long term acute care facilities, skilled nursing facilities, or acute rehabilitation facilities) prior to the Day 8, Day 15 or Day 29 assessment, we will perform these assessments via telephone follow-up. The Day 8 call window will be Day 8 through 14. The Day 15 call window will be Day 15 through 22. The Day 29 call window will be Day 29 through 36. During these telephone calls, we will interview the patient, LAR, or facility staff to assess:

- Date of death (if applicable)
- ED visits and hospital readmissions after hospital discharge
- Location at the time of the call (home, long term acute care facility, skilled nursing facility, acute rehabilitation facility, hospital)
- Selected non-laboratory safety outcomes after hospital discharge
- COVID-19 7-point Ordinal Clinical Progression Outcomes Scale

The follow-up period for vital status (dead versus alive) is through Study Day 29. For most patients, we will establish vital status during the Study Day 29 visit (either in person for those who remain in the hospital or by phone for those who have been discharged). For patients who are not reached for the Study Day 29 visit, we will seek to establish vital status via phone calls, emails, and searches through medical records, obituaries, social media, and other sources.

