8.3.2 Missing data

We anticipate rare or no missingness for data points during a patients in-hospital course. There may be missing data for the COVID-19 7-point Ordinal Clinical Progression Outcomes Scale score after hospital discharge, which relies on phone follow-up. After discharge, distinguishing between category 1 and category 2 on the scale requires speaking to the participant or surrogate about normal daily activities. If the patient is not reached for follow-up phone calls after discharge, the COVID-19 7-point Ordinal Clinical Progression Outcomes Scale score will be classified as category 2 (not hospitalized, but unable to resume normal activities). If the patient is reached for a follow-up call post-charge and reports category 1, this classification of category 1 will be carried forward to future follow-up calls if the patient cannot be reached. For example, if the patient cannot be reached for the Day 8, 15, or 29 follow-up calls, a category 2 score will be reported for all three visits. If the patient is successfully contacted on the Day 8 call and reports category 1, and then the patient cannot be reached for a Day 15 call, the category 1 score from Day 8 will be carried forward to Day 15.

Missing data for a covariate used in the primary model will be multiply imputed using predictive mean matching if number of observations missing covariate values exceeds 5 percent. If fewer than 5% of observations have missing covariate values, missing values will be imputed with a single conditional mean.

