6.4 Outcomes with a competing risk of death

Some secondary outcomes, like the primary outcome, incorporate death as part of the scale. Others, such as length of hospital stay, do not. Because death censors length of stay, it is a competing outcome. Outcomes with a competing risk of death will be analyzed with a multi-state model. Both the instantaneous risk and cumulative risk of the outcome will be reported.

7 Safety Outcomes and Adverse Events

The frequency and description of safety outcomes and adverse events will be reported for all enrolled patients grouped by treatment assignment. The association between treatment received and safety

outcomes between groups will be estimated without covariate adjustment. The following table lists the safety outcomes and the planned analyses.

Outcome	Type	Analysis
Receipt of renal replacement therapy	Binary	Risk difference
Documented venous thromboembolic disease (DVT or PE)	Binary	Risk difference
Documented cardiovascular event (myocardial infarction or ischemic stroke)	Binary	Risk difference
Transfusion reaction	Binary	Risk difference
Transfusion related acute lung injury (TRALI)	Binary	Risk difference
Transfusion associated circulatory overload (TACO)	Binary	Risk difference
Transfusion related infection	Binary	Risk difference

8 Definition of the Primary Outcome

The primary outcome is patients' clinical status 14 days after randomization (measured on Study Day 15) as assessed with the seven-category COVID Ordinal Outcome Scale:

- Not hospitalized without limitation in activity
- Not hospitalized with limitation in activity
- Hospitalized not on supplemental oxygen
- Hospitalized on supplemental oxygen
- Hospitalized on non-invasive ventilation or high-flow nasal cannula
- Hospitalized on invasive mechanical ventilation or extracorporeal membrane oxygenation
- Death

While patients are in the hospital, primary outcome assessment will be performed by review of the electronic health records. For patients discharged prior to 14 days after randomization, study staff will call patients or their surrogates to obtain the patients' clinical status for primary outcome assignment.

9 Definition of SOFA Score

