10.1 All-location, all-cause 14-day mortality

All location, all cause 14-day mortality is defined as death between randomization and 14 days after randomization from any cause and in any location, including after discharge from the index hospitalization. Data on death will be collected from the electronic health record during the hospitalization and then from telephone calls to the patient or surrogate after discharge on Study Day 8, 15 and 29.

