10.2 All-location, all-cause 28-day mortality

All location, all cause 28-day mortality is defined as death between randomization and 28 days after randomization from any cause and in any location, including after discharge from the index hospitalization. Data on death will be collected from the electronic health record during the hospitalization and then from telephone calls to the patient or surrogate after discharge on Study Day 8, 15 and 29.

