This outcome is defined as clinical status 7 days after randomization (measured on Study Day 8) as assessed with the seven-category COVID Ordinal Outcome Scale, as described in the section on the Primary Outcome. Data on clinical status is collected from the electronic health record during the hospitalization and then from telephone calls to the patient or surrogate after discharge from the index hospitalization.

10.8 COVID Ordinal Outcomes Scale on Study Day 29

This outcome is defined as clinical status 28 days after randomization (measured on Study Day 29) as assessed with the seven-category COVID Ordinal Outcome Scale, as described in the section on the Primary Outcome. Data on clinical status were collected from the electronic health record during the hospitalization and then from telephone calls to the patient or surrogate after discharge from the index

hospitalization. Missing data for the COVID Ordinal Outcomes Scale on Day 29 will be handled in the same fashion as described for the primary outcome.

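### Could a discharged patient who died by Day 15 be scored category 1 or 2 in the primary outcome because the phone call failed?

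*SAP*

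**What the plan says.** SAP 3.2 (Missing data) opens by limiting its subject: "There may be missing data for the COVID-19 7-point Ordinal Clinical Progression Outcomes Scale score after hospital discharge, which relies on phone follow-up". It explains that telling category 1 from category 2 needs a conversation about daily activities. Two rules follow, and Protocol 8.3.2 repeats them. The first starts "If the patient is not reached for follow-up phone calls after discharge" and assigns category 2. The second carries an earlier category 1 forward; in the worked example, a patient reports category 1 on Day 8, and then if "the patient cannot be reached for a Day 15 call, the category 1 score from Day 8 will be carried forward to Day 15". SAP 10.8 (ordinal scale on Study Day 29) extends this: "Missing data for the COVID Ordinal Outcomes Scale on Day 29 will be handled in the same fashion as described for the primary outcome".

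The mortality outcomes draw on wider information. SAP 10.1 takes deaths from the hospital record and "then from telephone calls to the patient or surrogate after discharge on Study Day 8, 15 and 29". SAP 10.2 counts "death between randomization and 28 days after randomization from any cause and in any location". Protocol 7.3.1 asks for the date of death on follow-up calls and adds a search: "For patients who are not reached for the Study Day 29 visit, we will seek to establish vital status via phone calls, emails", followed by records, obituaries and other sources.

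On the scale itself, category 7 is death (Protocol 6.1, SAP 8), and SAP 6.4 says "Some secondary outcomes, like the primary outcome, incorporate death as part of the scale". SAP 3 places the primary analysis after follow-up and data lock are complete for all subjects.

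**The concern.** The only trigger in the two rules is failure to reach the patient; vital status is not mentioned. Take a patient who reports category 1 on the Day 8 call, dies on Day 12 and is not reached for the Day 15 call. A relative reports the death on the Day 29 call. SAP 10.1 counts a 14-day death. SAP 3.2, followed word for word, gives a Day 15 score of 1. Without the Day 8 report the score would be 2. The Day 29 scale could conflict with 28-day mortality in the same way when the vital-status search finds a death in a patient who never answered a call.

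If that happened, the worst outcome would be recorded as the best or second best, and two outcomes in one report would contradict each other. The trial also judges efficacy against a fixed likelihood ratio of 7, so a few miscoded deaths falling in one arm could matter in a close result.

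**Working it through.** **1. What the text settles.**

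| Question | Where | Answer |
|---|---|---|
| What does the rule cover? | SAP 3.2, heading and opening; SAP 10.8 | Missing scores |
| Why is a score missing? | SAP 3.2 | No one to ask about normal activities (1 versus 2) |
| Is death on the scale? | Protocol 6.1, SAP 6.4, SAP 8 | Yes, category 7 |
| When are scores analysed? | SAP 3 | After complete follow-up and data lock |
| Is the date of death available by then? | Protocol 7.3.1, SAP 10.1 | Yes, from calls or, for patients not reached at Day 29, the search |
| Is a rule-assigned score frozen at Day 15? | – | Nowhere stated |

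A death dated on or before Day 15 and known before lock fixes the score at 7. Nothing is then missing, and the rule has nothing to fill.

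**2. How narrow the route is.** The category 1 case needs discharge before the Day 8 call, a report of normal activities on that call (window Day 8–14), death by Day 15, no contact with the patient, a representative or facility staff through Day 22 (Protocol 7.3.1), and later discovery of the death. Patients who cannot be contacted on Day 29–36 are excluded at entry (Protocol 4.2). The category 2 case drops only the Day 8 report.

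**3. Size if the literal reading were applied.** The documents give no non-contact rate, no post-discharge death rate and no control distribution, so these are assumptions:

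- Control proportions for categories 1–7: (a) .25, .40, .05, .08, .05, .07, .10; (b) .40, .25, .05, .08, .05, .07, .10; (c) .15, .40, .06, .09, .06, .09, .15.
- 500 patients per arm and a true odds ratio of 0.73 (SAP 4).
- A fraction *f* of deaths in each arm is miscoded, half to category 1 and half to category 2.

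Deaths in the plasma arm: for (a) and (b), odds 0.10/0.90 × 0.73 = 0.0811, risk 0.0811/1.0811 = 0.0750, so 37.5 deaths against 50 in controls, 87.5 in all. For (c), odds 0.15/0.85 × 0.73 = 0.1288, risk 0.1141, so 57.1 against 75, 132.1 in all.

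Power: a likelihood ratio of 7 corresponds to |z| = √(2 ln 7) = 1.973. The plan's 80% power at 0.73 implies a standard error of 0.3147/(1.973 + 0.842) = 0.1118. Power at another odds ratio is Φ(|ln OR|/0.1118 − 1.973). Example: OR 0.7349 gives 0.3080/0.1118 − 1.973 = 0.782, power 0.783.

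Large-sample proportional-odds fits to the altered distributions give:

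| *f* | Deaths miscoded per 1000 | Fitted OR | Power |
|---|---|---|---|
| 0 | 0 | 0.730 | 0.800 |
| 2% | 1.8–2.6 | 0.7309–0.7320 | 0.793–0.797 |
| 5% | 4.4–6.6 | 0.7321–0.7349 | 0.783–0.793 |
| 10% | 8.8–13.2 | 0.7343–0.7398 | 0.765–0.785 |

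These are upper bounds, because a death that is never discovered is scored 1 or 2 under either reading. For scale, the plan's power rests on 1000 simulated datasets per effect size (SAP 4), with a Monte Carlo standard error of √(0.8 × 0.2/1000) = 0.013. The shift at 2% is well inside that, and the shift at 5% is at most 0.017.

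**4. Miscoding in one arm only.** With 500 per arm, assumed control death rates of 10–15% and a true odds ratio of about 0.78, the fitted likelihood ratio without miscoding is 12.5–16.7. Moving three control deaths to category 2, and none in the plasma arm, gives 9.1–9.9. Moving five gives 7.0–7.4. Equal numbers in both arms (2 or 5 each) change the fitted odds ratio by at most 0.004.

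**The case for a change.** The best argument for a change is that the SAP is explicit on this point elsewhere, and in both directions. SAP 10.9 combines in-hospital support data with deaths from all locations and says outright that a death before Study Day 29 sets the free-day count to zero. SAP 10.5 says the opposite for time to recovery, which ignores death after discharge. For the primary outcome the missing-data rule is silent, and SAP 8 names only calls to patients or surrogates as the source after discharge. The SAP 3.2 example of a patient missed at all three calls also describes the people whom Protocol 7.3.1 sends to the vital-status search.

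It stands that no sentence states the override, and that a one-sided run of miscoded deaths could bring a moderately positive result close to the threshold of 7. It does not follow that the rule is open. Free days and time to recovery are built from in-hospital data, so each definition has to say whether a later death counts. The ordinal scale has death as its own category, so the definition already answers the question. In the one-sided example the likelihood ratio still does not fall below 7, and reaching 7.0–7.4 takes five known deaths coded as alive in one arm and none in the other. Protocol 7.2 also places variable definitions for site staff in a manual of operations or the data capture system, which are not among the documents, so case-by-case scoring is not shown.

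**Conclusion.** The observation about the wording is correct: neither SAP 3.2 nor Protocol 8.3.2 says in words that a known death overrides the category 2 default or the carried-forward category 1. It does not call for a change. The heading, the stated purpose of the rule, the definition of category 7, SAP 6.4 and the timing of the analysis all lead to the same coding, and an analyst holding a date of death on or before the assessment day would score 7. The same reading covers Day 29 through SAP 10.8.

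Even if the literal reading were applied, the effect would be very small under equal miscoding: an odds ratio of 0.731–0.735 in place of 0.73 and power of about 78–80% when 2–5% of Day 15 deaths are affected, and at most 0.740 and about 76% when 10% are. Those figures rest on assumed control distributions, assumed rates and an even split between categories 1 and 2. A clarifying sentence would do no harm, but it would only record what the plan already implies.
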